6.1.5.3 Rationale for Dosing Frequency

The QW dosing frequency was selected using preliminary Phase 1 PK data (Study 391101) showing that optimal tissue saturation could be obtained with the QW dosing relative to the Q2W dosing. The half-life of imalumab ranged from 3.3 to 10.8 days (ie, around a range of approximately 1 week), indicating that QW dosing is preferable to Q2W dosing for maintaining more stable concentrations of imalumab. For

the 10 mg/kg dose, C_{\max}/C_{\min} ratios (peak/trough fluctuation) on Day 15 of Cycle 2 were approximately 4-fold for QW dosing compared with 7.5-fold for Q2W dosing.

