the end of the dosing phase, microscopic findings were confined to the synovial membrane and adjacent ligaments and/or tendons in single or multiple joints, including the knee, elbow, tarsus, and phalanges of 3 intermediate-dose group and 6 high-dose group animals. These lesions were attributed to administration of imalumab. Findings consisted of subacute inflammation and villous hyperplasia of the synovial membrane (in the knee, elbow, and tarsus joints), subacute inflammation of the ligament (in the knee) and subacute inflammation of the ligament and of the tendon sheath (in the tarsus). In the phalanges of the hand and foot, subacute inflammation of the tendons and tendon sheath and/or subacute inflammation and villous hyperplasia of the synovial membrane and/or sub-acute inflammation of the ligament were also noted. The severity and incidence of the findings were more prominent in male animals. After the recovery phase, histopathological findings in 1 intermediate-dose group and 2 high-dose group animals were present in the larger joints (knee, elbow, and tarsus), as well as in the middle finger and little toe. These consisted of villous hyperplasia and inflammation of the synovial membranes and inflammation of the ligament and tendon, which was also seen in terminal killed animals. In addition to the above findings, ossification of the tendon sheath (tarsus) and ligament (elbow) was restricted to 1 high-dose group female of the recovery phase.

In rats, no adverse effects were detected following 5 consecutive weekly doses of up to 250 mg/kg imalumab over a period of 1 month.

In summary, while no NOAEL was observed during the single-dose studies, repeat-dose toxicity studies in rats and cynomolgus monkeys demonstrated a NOAEL of 250 mg/kg in rats and 25 mg/kg (1 month) and 10 mg/kg (6 months) in cynomolgus monkeys.

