9. SUBJECT SELECTION, WITHDRAWAL, AND DISCONTINUATION

9.1 Inclusion Criteria

Subjects who meet **ALL** of the following criteria are eligible for this study:

1. Provision of a signed informed consent
2. Male and female subjects 18 years of age and older at the time of screening
3. Subjects who progressed after receiving at least 2, but no more than 3, prior cancer drug therapy treatment lines including SoC in the metastatic setting
4. Anticipated life expectancy >3 months at the time of screening
5. Weight between 40 kg and 180 kg
6. Histologically or cytologically confirmed diagnosis of CRC
7. Metastatic CRC not amenable to surgical resection
8. Known KRAS, NRAS mutation status (if unknown status for either of these genes, and no archival tissue is available, a fresh tumor biopsy will be obtained)
9. At least 1 measurable lesion as defined by RECIST v1.1
10. ECOG PS of 0-2
11. Adequate hematological function, defined as:
 - a. Platelet count \geq 100,000/ μ L
 - b. Prothrombin time and activated partial thromboplastin time (aPTT) $<$ 1.5 times the upper limit of normal (ULN)
 - c. Absolute neutrophil count (ANC) \geq 1000/ μ L
 - d. Hemoglobin \geq 9 g/dL, without the need for transfusion in the 2 weeks prior to screening
12. Adequate renal function, defined as serum creatinine \leq 2.0 times ULN and creatinine clearance $>$ 50 mL/min or estimated glomerular filtration rate $>$ 50 mL/min/1.73 m²
13. Adequate liver function, defined as:
 - a. Aspartate aminotransferase (AST) and alanine aminotransferase (ALT) \leq 2.5 times ULN for subjects without liver metastases, or \leq 5 times ULN in the presence of liver metastases
 - b. Bilirubin \leq 2.0 times ULN, unless subject has known Gilbert's syndrome
14. Adequate venous access

15. For female subjects of childbearing potential, the subject presents with a negative serum pregnancy test at screening and agrees to employ 2 forms of adequate birth control measures, including at least 1 barrier method (eg, diaphragm with spermicidal jelly or foam, or [for male partner] condom) throughout the course of the study and for at least 90 days after the last administration of imalumab. In addition, these birth control methods must be continued for at least 180 days after last administration of 5-FU in subjects who receive this treatment. Secondary contraceptive measures could be either birth control pills, patches, or intrauterine devices

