10.4 Medications and Non-Drug Therapies

During the study, subjects are expected to be on concomitant medication(s) if they are given treatment for any underlying medical conditions, provided the medications are not anticancer therapies. Subjects may take additional concomitant medication(s) as needed for medical management during this study. If growth factor medications are to be administered, they should be used in accordance with local best practice. All concomitant medication use should be recorded.

The following medications and non-drug therapies are **not** permitted within 4 weeks (< 28 days) prior to study drug administration and during the course of the study:

- Medications:
 - Antitumor therapy, including chemotherapy, radiotherapy, antibody therapy, molecular targeted therapy, retinoid therapy, or hormonal therapy
 - Brivudin, sorivudine, and other nucleoside analogues must be avoided in subjects who receive treatment with 5-FU
 - Live vaccines must be avoided for 6 weeks following last dose of imalumab
 - Other investigational product
- Non-drug therapies:
 - Major surgery
 - Investigational device

The following medications are **not** permitted within 4 weeks (< 28 days) prior to C1D1 and during the course of the study:

- Live vaccines

A subject who has taken any of these medications or received any of these non-drug therapies must be discontinued.

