12.1.2 Assessment of Adverse Events

For the purposes of this study, each non-serious untoward medical occurrence experienced by a subject undergoing study-related procedure(s) before first exposure to IP will be recorded on the AE CRF; however, these events will not be considered as AEs and will not be included in the analysis of AEs.

Each TEAE (non-serious AE or SAE) from the first IP exposure until study completion/discontinuation or 30 days (± 7 days) following the last IP treatment will be described on the AE CRF using the medical diagnosis (preferred), or, if no diagnosis could be established at the time of reporting the AE, a symptom or sign, in standard medical terminology in order to avoid the use of vague, ambiguous, or colloquial expressions (see definition in Section 12.1). Each AE will be evaluated by the investigator for:

- Seriousness as defined in Section 12.1.1.1
- Severity as defined in Section 12.1.2.1
- Causal relationship to IP exposure or study procedure as defined in Section 12.1.2.2.

For each AE, the outcome (ie, recovering/resolving, recovered/resolved, recovered/resolved with sequelae, not recovered/not resolved, fatal, unknown) and if applicable action taken (ie, dose increased, dose not changed, dose reduced, drug interrupted, drug withdrawn, not applicable, or unknown) will also be recorded on the AE CRF. Recovering/resolving AEs will be followed until resolution, medically stabilized, or 30 days after the last IP administration, whichever comes first. If the severity rating for an ongoing AE changes before the event resolves, the original AE report will be revised (ie, the event will not be reported as separate AE). During the course of any AE, the highest severity rating will be reported.

Deviations from the protocol-specified dosage (including overdosing [any dose that is at least 20% higher than the highest explored dose level], underdosing [any dose that is lower than the intended explored dose level by 10%], abuse, and withdrawal [see

Section 9.3]), treatment errors (including incorrect route of administration, use of an incorrect product, and deviations from the protocol-defined dosing schedule), failures of expected pharmacological actions, and unexpected therapeutic or clinical benefits will be followed with regard to occurrence of AEs, lack of efficacy, and/or other observations because these events may be reportable to regulatory authorities.

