Any pregnancy of the subject or partner that is confirmed within 90 days after administration of imalumab will be reported on a Pregnancy Form and followed up at estimated date of delivery and 1 year postdelivery, if feasible.

If an investigator becomes aware of an SAE occurring in a subject after study completion, the SAE must be reported on the provided Serious Adverse Event Report (SAER) Form within 24 hours after awareness; no additional reporting on CRFs is necessary.

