Urine sample for genetic biomarkers (cfDNA) ^m	X					Day 28 of Cycle 1 and then every other cycle	X	

Table 3 Schedule of Study Procedures and Assessments: Parts 1 and 2								
Trial Periods	Screening Visit	Baseline Visit	Study Visits Per Treatment Cycle ^a				End of Study/ Early Termination Visit	Safety Follow-Up Visit ^b
Study Days	Days -28 to -1	Day 1 Predose	Days 1 to 7	Days 8 to 14	Days 15 to 21	Days 22 to 28		
Treatment Schedule								
Adverse events ⁿ	X	X	X	X	X	X	X	X
Concomitant medications/non-drug therapies	X	X	X	X	X	X	X	X

Abbreviations: 5-FU=5-fluorouracil; ADA=anti-drug antibody; AE=adverse event; C1D1=Cycle 1 Day 1; cfDNA=cell-free DNA; CT=computerized tomography; ECG=electrocardiogram; ECHO=echocardiogram; ECOG PS=Eastern Cooperative Oncology Group Performance Status; EORTC QLQ-C30=European Organization for Research and Treatment of Cancer Quality of Life Questionnaire Core 30; EORTC QLQ-CR29=European Organization for Research and Treatment of Cancer Quality of Life Questionnaire for colorectal cancer 29; EQ-5D=European Quality of Life – 5 Dimensions; IRT=Interactive Response Technology; KRAS=Kirsten rat sarcoma viral oncogene homolog; LV=leucovorin; MIF=macrophage migration inhibitory factor; MRI=magnetic resonance imaging; MUGA=multigated acquisition scan; NADA=neutralizing anti-drug antibody; NRAS=neuroblastoma RAS viral (v-ras) oncogene homolog; oxMIF=oxidated macrophage migration inhibitory factor; PD=pharmacodynamic; PK=pharmacokinetic; Q2W=every 2 weeks; QW=every week; RECIST=Response Evaluation Criteria in Solid Tumors; SoC=standard of care.

^a Treatment cycles are defined in this study as 4-week cycles. In each treatment cycle, imalumab is administered QW, and 5-FU/LV and panitumumab are administered Q2W in 4-week cycles. Treatment cycles will continue until progression, unacceptable toxicities, or withdrawal of consent.

^b The Safety Follow-up Visit should occur 30 (± 7) days after the last dose of study treatment. For subjects who have stopped study drug or have documented disease progression, post-study telephone calls to assess overall survival will be made by site staff every 3 months.

^c Subject informed consent occurs at screening, prior to any study-specific procedure.

^d IRT will be utilized at screening and baseline visits for all subjects (Part 1 and Part 2), at all subsequent study visits in Part 1, and all subsequent study visits in Part 2 for subjects in Arm A only.

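### Pregnancy reporting closes 90 days after imalumab although contraception is required for 180 days after 5-FU, and Arm B has no reporting window after treatment

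*Protocol*

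**What the plan says.** **Pregnancy.** Protocol Section 12.1.2 states: "Any pregnancy of the subject or partner that is confirmed within 90 days after administration of imalumab will be reported on a Pregnancy Form". Such pregnancies are then followed to the expected delivery date and one year beyond, if feasible. Section 9.1 (inclusion criteria 15 for women and 16 for men) requires contraception for at least 90 days after imalumab and adds, for those who receive 5-FU, that "these birth control methods must be continued for at least 180 days after last administration of 5-FU". SAP Section 2.2.1 repeats these criteria and adds no reporting rule.

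Three other provisions bear on this:
- Section 9.3 covers a subject who becomes pregnant while in the study, with follow-up to one year after delivery if feasible. It does not mention partners.
- Section 12.1.1.1 classes pregnancy complications and terminations as SAEs, but not uncomplicated pregnancies.
- Section 12.1.2 requires reporting of an SAE in a subject if the investigator learns of it after study completion.

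The last scheduled pregnancy test is at the Safety Follow-up visit (Section 12.7.2).

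**Adverse events.** Section 12.1.2 states: "Recovering/resolving AEs will be followed until resolution, medically stabilized, or 30 days after the last IP administration, whichever comes first". The same section collects treatment-emergent events until 30 (±7) days after the last dose. Section 20.2 gives the matching visit: "The Safety Follow-up Visit should occur 30 (± 7) days after the last dose of study treatment". The outcome codes include "recovered/resolved with sequelae, not recovered/not resolved, fatal, unknown". After that visit, Section 10.3.3.10 provides telephone calls every 3 months, for survival only.

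**The concern.** The protocol accepts that 5-FU carries a reproductive precaution for 180 days, yet its only post-treatment pregnancy rule is tied to another drug and runs half as long. A subject or partner who conceives in the later part of the 5-FU period, and whose pregnancy is uncomplicated, generates no required record. No scheduled test would find it. At stake is the exposure and outcome record for these pregnancies, maternal and paternal, and a like-for-like record in the two arms.

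The AE rule raises a smaller question of the same kind. A fixed stop at day 30 does not fit a collection window that can run past it, and the text makes no exception for a drug-related SAE that is still open.

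**Working it through.** No sample size, power or event count lies behind these windows, so there is no plan figure to reproduce. The check sets the stated windows side by side.

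**1. Length of the pregnancy gap.** Let I be the day of the last imalumab dose and F the day the last 5-FU infusion ends, on one calendar. Reporting ends at I + 90 and the 5-FU contraception period ends at F + 180.

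Gap = (F + 180) − (I + 90) = 90 + F − I.

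- Both counted from the same day: 180 − 90 = 90 days, half of the 180.
- Both started on Day 1, with 5-FU ending on Day 3 (2 hours of LV, then 46 hours of 5-FU): 183 − 91 = 92 days.
- Imalumab on Day 22, 5-FU given on Days 15 to 17: 197 − 112 = 85 days.

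Section 10.3.3.1 lets imalumab continue while 5-FU is interrupted. If 5-FU is not resumed, each further day of imalumab shortens the gap by one day.

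**2. Trigger.** The rule turns on the date of confirmation, not of conception. A conception inside the 90 days but confirmed on day 91 or later falls outside it. This affects every imalumab recipient, with or without 5-FU.

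**3. Who is covered after treatment.**

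| Group | Reporting window | Stated contraception period | Uncovered |
|---|---|---|---|
| Part 1 and Arm A, imalumab + 5-FU/LV | 90 days after imalumab | 180 days after 5-FU | 85 to 92 days |
| Part 1 and Arm A, imalumab + panitumumab | 90 days | 90 days after imalumab | late confirmations only |
| Arm B, SoC includes 5-FU | none | 180 days after 5-FU | all 180 days |
| Arm B, other SoC | none | none stated after treatment | no rule to compare |

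**4. AE windows.** The safety visit falls between day 30 − 7 = 23 and day 30 + 7 = 37. Follow-up stops at day 30 at the latest. An event starting on days 31 to 37 is collected when its follow-up has already expired, a mismatch of 37 − 30 = 7 days. The follow-up sentence also names only events that are recovering or resolving; events that are not recovering have no stated rule.

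**5. Other time spans in the protocol, against day 30.** Residual drug at day 30 is 0.5^(30/half-life), assuming a single terminal half-life.

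- Half-life 3.3 days: 0.2% remains; five half-lives take 16.5 days.
- Half-life 8.1 days: 7.7% remains; five half-lives take 40.5 days.
- Half-life 10.8 days: 14.6% remains; five half-lives take 54 days.
- Live-vaccine precaution: 42 − 30 = 12 days later than the stop.
- Monkey recovery period in the 6-month study: 56 − 30 = 26 days later than the stop.

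**The case against.** On pregnancy, the best defence is that a contraception period is not automatically a reporting window. The protocol's summary of changes (item 7) shows that the 180 days were added as contraceptive advice to match the 5-FU product information. Complications and terminations remain SAEs, and pregnancies during the study are followed under Section 9.3. All of this is true and narrows the point to uncomplicated pregnancies after treatment, plus partner pregnancies. It does not remove it. For imalumab the protocol sets both periods at 90 days, and nothing explains why 5-FU differs. The late-SAE rule is passive and does not reach an uncomplicated pregnancy.

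On adverse events, a reader might infer that the 30-day stop falls inside a risk period for joint toxicity and that unresolved joint events are lost. The documents do not support that:

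- No section states a post-dose risk period for AEs or joint events. "Live vaccines must be avoided for 6 weeks following last dose of imalumab" is a vaccination precaution.
- The animal finding, "After the recovery phase, histopathological findings in 1 intermediate-dose group and 2 high-dose group animals were present in the larger joints", is microscopic and arose at 25 and 50 mg/kg weekly for 26 weeks. The 6-month NOAEL was 10 mg/kg (Section 6.4.1). AE follow-up of any length would not show synovial histology.
- None of 48 treated humans had drug-related joint inflammation (Section 6.5).
- "The half-life of imalumab ranged from 3.3 to 10.8 days", so 30 days is ample at the short end. It is less so at the long end, and Section 6.4.2.1.2 warns that longer estimates may be too low.
- An unresolved event stays on the CRF with that outcome. SAEs volunteered within 30 days of the last visit are also collected (Section 12.1.2.3), which can reach 37 + 30 = day 67, and later ones are reportable if the investigator learns of them.

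What stands is the mismatch between day 30 and day 37, and the absence of any exception for related SAEs.

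**Conclusion.** The pregnancy point holds. Sections 9.1 and 12.1.2 do not fit together and must be reconciled. For subjects given imalumab with 5-FU, about 90 days (85 to 92) of the stated 5-FU contraception period have no reporting rule for uncomplicated pregnancies. Arm B has no window after treatment, and confirmation-based timing excludes late conceptions in all imalumab recipients. The range assumes that both drugs stop in the same cycle and that the 90 days run from the last imalumab dose, which the sentence does not say outright. The documents give no basis for estimating how many pregnancies would be affected.

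The AE point holds only as a secondary one: two windows in one section disagree by up to 7 days, and the later course of a related SAE still open at day 30 need not be recorded. This is incomplete follow-up, not loss of the event. Neither point affects the PFS comparison; the gain is in safety data, small but cheap.

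**What to change.** - **Pregnancy Form rule (12.1.2).** Reconcile it with criteria 15 and 16 in Section 9.1. Cover any pregnancy of a subject or partner conceived within the contraception period the protocol already states for the study drugs received, in both arms, whenever it is confirmed. For Arm B subjects on drugs with no stated period, say which reporting window applies.
- **AE follow-up rule (12.1.2).** Align the day-30 stop with the 30 (±7)-day collection window, and say what applies to events that are not recovering. For SAEs related to study drug that are open at the Safety Follow-up visit, record the final outcome and its date.
- **Survival calls (10.3.3.10).** Add a pregnancy question and an open-SAE question. Two calls at 3-month spacing reach about 180 days; a conception near the end of that period may surface only at the third.

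The cost is protocol wording, a few CRF fields and slightly more data collection after treatment. Restricting the AE change to related SAEs avoids open-ended follow-up of every minor event. No new visits or procedures are needed.

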12.1.2.1 Severity

The investigator will assess the severity of each AE using his/her clinical expertise and judgment based on the NCI CTCAE v4.03. In the event an AE is not described in the NCI CTCAE v4.03, the severity grades will be mapped to the following terms:

Table 2 Mapping Conventions for AE Severity (For AEs Not Described Within NCI CTCAE)	
NCI CTCAE Grade	Corresponding AE Severity (if Not Provided in NCI CTCAE)
Grade 1	Mild; asymptomatic or mild symptoms; clinical or diagnostic observations only; intervention not indicated
Grade 2	Moderate; minimal, local, or noninvasive intervention indicated; limiting age-appropriate instrumental activities of daily living (ADL)
Grade 3	Severe or medically significant but not immediately life-threatening; hospitalization or prolongation of hospitalization indicated; disabling; limiting self-care ADL
Grade 4	Life-threatening consequences; urgent intervention indicated
Grade 5	Death related to AE

Abbreviations: AE=adverse event; NCI CTCAE=National Cancer Institute Common Terminology Criteria for Adverse Events.

12.1.2.2 Causality

Causality is a determination of whether there is a reasonable possibility that the IP is etiologically related to/associated with the AE. Causality assessment includes, eg, assessment of temporal relationships, dechallenge/rechallenge information, association (or lack of association) with underlying disease, presence (or absence) of a more likely cause, and physiological plausibility. For each AE, the investigator will assess the causal relationship between the IP and the AE using his/her clinical expertise and judgment according to the following most appropriate algorithm for the circumstances of the AE:

- Not related (both circumstances must be met)
 - Is due to underlying or concurrent illness, complications, concurrent treatments, or effects of concurrent drugs
 - Is not associated with the IP (ie, does not follow a reasonable temporal relationship to the administration of IP or has a much more likely alternative etiology)
- Unlikely related (either 1 or both circumstances are met)
 - Has little or no temporal relationship to the IP
 - A more likely alternative etiology exists
- Possibly related (both circumstances must be met)
 - Follows a reasonable temporal relationship to the administration of IP
 - An alternative etiology is equally or less likely compared to the potential relationship to the IP
- Probably related (both circumstances must be met)
 - Follows a strong temporal relationship to the administration of IP, which may include but is not limited to the following:
 - Reappearance of a similar reaction upon re-administration (positive rechallenge)
 - Positive results in a drug sensitivity test (skin test, etc.)
 - Toxic level of the IP as evidenced by measurement of the IP concentrations in the blood or other bodily fluid
- Another etiology is unlikely or significantly less likely

For events assessed as not related or unlikely related and occurring within 5 days, the investigator shall provide the alternative etiology. These causality definitions will also be used to assess the relationship of an AE with a study-related procedure(s), if necessary.

